5.7.4. Biological samples evaluation

5.7.4.1. Immunological read-outs

In case of insufficient blood sample volume to perform assays for all antibodies, the samples will be analysed according to priority ranking provided in [Table 12](#).

Table 12 Immunological read-outs (Amended 06 September 2016)

Blood sampling timepoint		No. subjects	Component	Components priority rank
Type of contact and timepoint	Sampling timepoint			
Visit 1 (Day 0)	Pre-Pri	All	PT, FHA, PRN	1
			D, T	2
Visit 4 (Month 3 or Month 5)*	Post-Pri	All	PT, FHA, PRN	1
			HBs, PRP	2
			D, T	3
			Poliovirus types 1, 2, 3	4
			13 pneumococcal serotypes	5

Pre-Pri: Blood sample to be collected before the first dose of the primary vaccination course.

Post-Pri: Blood sample to be collected one month after the last dose of the primary vaccination course, depending on the vaccination schedule.

* *Depending on the vaccination schedule*

5.7.5. Immunological correlates of protection

The following cut-offs are accepted as immunological correlates of protection:

- Specific antibodies against diphtheria toxoid (anti-diphtheria) and tetanus toxoid (anti-tetanus) will be measured by Enzyme-linked immunosorbent assay (ELISA). The assay cut-off of ELISA is currently set at 0.1 International Units per ml (IU/ml), which provides a conservative estimate of the percentage of subjects deemed to be protected [[Camargo, 1984](#); [Melville-Smith, 1983](#)].

- Antibodies against the hepatitis B surface antigen (anti-HBs) will be measured using ChemiLuminescence ImmunoAssay (CLIA). The cut-off of the test is set at 6.2 mIU/ml. An antibody concentration ≥ 10 mIU/ml defines seroprotection [[CDC](#), 1991].
- Antibodies against poliovirus types 1, 2 and 3 will be determined by a virus micro-neutralisation test adapted from the World Health Organization Guidelines for WHO/EPI Collaborative Studies on Poliomyelitis [[WHO](#), 1993]. Titres will be expressed in terms of the reciprocal of the dilution resulting in 50% inhibition. Antibody titres greater than or equal to 1:8 are considered as protective.
- Data from subjects given unconjugated Hib vaccine suggest that, in the absence of induction of immunological memory, a concentration of 0.15 $\mu\text{g/mL}$ is indicative of short-term protection, with 1 $\mu\text{g/mL}$ considered indicative of long-term protection [[Käyhty](#), 1983; [Anderson](#), 1984].
- No serological correlate of protection against pertussis has been established [[Plotkin](#), 2010]. Antibodies against the pertussis components pertussis toxoid (PT), filamentous haemagglutinin (FHA) and pertactin (PRN) will be measured by ELISA. The seropositivity cut-off for all three pertussis antibodies in ELISA is currently 5 EL.U/ml. Subjects with antibody concentration below the cut-off will be considered seronegative.
- Pneumococcal serotype specific total immunoglobulin G (IgG) antibodies (antibodies to 1, 3, 4, 5, 6A, 6B, 7F, 9V, 14, 18C, 19A, 19F and 23F) will be each measured by 22F-inhibition ELISA [[Concepcion](#), 2001] or multiplex assay. The antibody concentration for ELISA will be determined by logistic log comparison of the ELISA curves with a standard reference serum 89-SF available from the US Food and Drug Administration for which concentration of IgG and IgM to the serotypes are known in $\mu\text{g/ml}$ [[Quataert](#), 1995]. The cut-off for ELISA is 0.05 $\mu\text{g/ml}$. No correlate of protection is defined for the immune response to pneumococcal antigens. At the discretion of GSK Biologicals, this assay will be performed either at a GSK laboratory or at the WHO reference laboratory. The assay cut-off of the 22F-inhibition ELISA test performed at the WHO reference laboratory is 0.15 $\mu\text{g/ml}$.

The immunological assay results will be communicated to the investigator as soon as they become available.

The investigator is encouraged to share the immunological assay results for non-responders with the study subjects' parent(s)/LAR(s).

For the subjects identified as non-responders, it remains the responsibility of the investigator in charge of the subject's clinical management to determine the medical need for re-vaccination and to re-vaccinate the subjects as per local/regional practices.

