Rationale for the study and study design	
 • Rationale for the study 
Recent studies have shown that maternal combined reduced antigen content diphtheria-tetanus-acellular pertussis (dTpa) vaccination during pregnancy results in high pertussis antibody concentrations in infants during the period between birth and the first vaccine dose of Diphtheria-Tetanus-acellular Pertussis (DTPa) vaccination series. Although slightly decreased immune responses following the primary DTPa vaccination has been observed in infants whose mothers received dTpa vaccine compared to those whose mothers did not receive dTpa vaccine, the differences did not persist following the booster vaccination in infants [Hardy-Fairbanks, 2013; Gall, 2011].
 
An analysis of data from the Clinical Practice Research Datalink (a primary care database of 520 general medical practices in England) demonstrates that maternal dTpa immunisation can decrease the incidence of infant pertussis. After a maternal pertussis vaccination programme was introduced in October 2012 in response to a pertussis outbreak in England, the number of pertussis cases in infants younger than three months of age and the number of hospitalisations decreased significantly [Amirthalingam, 2014]. (Amended 06 September 2016)
 
In 2013, the Advisory Committee on Immunisation Practices (ACIP) recommended that all women should be vaccinated with dTpa vaccine during each pregnancy, regardless of the previous immunisation schedule [CDC, 2013b]. Similar recommendations have been implemented in many countries including UK, New Zealand, Israel, Mexico, Brazil, Colombia, Uruguay, Panama, Costa Rica, Argentina and some provinces in Australia and Spain [Joint Committee on Vaccination and Immunisation (JCVI), 2012; Pharmaceutical Management Agency (PHARMAC), 2012; TAG, 2013]. The National Advisory Committee on Immunisation in Canada

recommends that all pregnant women following 26 weeks of pregnancy who have not received a dose of pertussis-containing vaccine in adulthood should be encouraged to receive *dTpa* vaccination. In special circumstances, such as an outbreak situation, all pregnant women who are of 26 weeks gestation or greater may be offered *dTpa* vaccination irrespective of their immunisation history [Warshawsky, 2014; Public Health Agency of Canada, 2014]. (*Amended 06 September 2016*)

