1.2. Rationale for the study and study design

1.2.1. Rationale for the study

Recent studies have shown that maternal combined reduced antigen content diphtheria-tetanus-acellular pertussis (dTpa) vaccination during pregnancy, results in high pertussis

antibody concentrations in infants during the period between birth and the first vaccine dose of DTPa vaccination series. Although slightly decreased immune responses following the primary DTPa vaccination has been observed in infants whose mothers received dTpa vaccine compared to those whose mothers did not receive dTpa vaccine, the differences did not persist following the booster vaccination in infants [[Hardy-Fairbanks](#), 2013; [Gall](#), 2011].

An analysis of data from the Clinical Practice Research Datalink (a primary care database of 520 general medical practices in England) demonstrates that maternal *dTpa* immunisation can decrease the incidence of infant pertussis. After a maternal pertussis vaccination programme was introduced in October 2012 in response to a pertussis outbreak in England, the number of pertussis cases in infants younger than three months of age and the number of hospitalisations decreased significantly [[Amirthalingam](#), 2014]. **(Amended 06 September 2016)**

In 2013, the Advisory Committee on Immunization Practices (ACIP) recommended that all women should be vaccinated with dTpa vaccine during each pregnancy, regardless of the previous immunisation schedule [[CDC](#), 2013b]. Similar recommendations have been implemented in 18 countries including UK, New Zealand, Israel, Mexico, Brazil, Colombia, Uruguay, Panama, Costa Rica, Argentina and some provinces in Australia and Spain [Joint Committee on Vaccination and Immunization (JCVI), 2012; Pharmaceutical Management Agency (PHARMAC), 2012; [TAG](#), 2013]. The National Advisory Committee on Immunization in Canada recommends that all pregnant women following 26 weeks of pregnancy who have not received a dose of pertussis-containing vaccine in adulthood should be encouraged to receive *dTpa* vaccination. In special circumstances, such as an outbreak situation, all pregnant women who are of 26 weeks gestation or greater may be offered *dTpa* vaccination irrespective of their immunisation history [[Warszawsky](#), 2014; [Public Health Agency of Canada](#), 2014]. **(Amended 06 September 2016)**

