5.2.2. Randomisation of treatment

5.2.2.1. Treatment allocation to the subject

There will be no randomisation of subjects into groups in this study. The infants enrolled in this study will be allocated to the same groups as their mothers in the 116945 [DTPA (BOOSTRIX)-047] study. Subjects will retain the same subject number as their corresponding mothers from the 116945 [DTPA (BOOSTRIX)-047] study.

The treatment numbers will be allocated by dose.

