5.3. Method of blinding

This study will be conducted in an open-label manner since the treatment is similar between the two groups. Also, the data related to the study groups will be unblinded at the end of study 116945 [DTPA (BOOSTRIX)-047].

Note: The study personnel operating SBIR and the site staff will remain blinded towards the treatment allocation to subjects in study 116945 [DTPA (BOOSTRIX)-047].
(Amended 06 September 2016)

The laboratory in charge of the laboratory testing will be blinded to the treatment, and codes will be used to link the subject and study (without any link to the treatment attributed to the subject) to each sample.

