8.2.3.2. Assessment of adverse events**8.2.3.2.1. Assessment of intensity**

The intensity of the following solicited AEs will be assessed as described:

Table 20 Intensity scales for solicited symptoms in infants less than 6 years of age

Adverse Event	Intensity grade	Parameter
Pain at injection site	0	None
	1	Mild: Minor reaction to touch
	2	Moderate: Cries/protests on touch
	3	Severe: Cries when limb is moved/spontaneously painful
Redness at injection site		Record greatest surface diameter in mm
Swelling at injection site		Record greatest surface diameter in mm
Fever*		Record temperature in °C/°F
Irritability/Fussiness	0	Behaviour as usual
	1	Mild: Crying more than usual/no effect on normal activity
	2	Moderate: Crying more than usual/interferes with normal activity
	3	Severe: Crying that cannot be comforted/prevents normal activity
Drowsiness	0	Behaviour as usual
	1	Mild: Drowsiness easily tolerated
	2	Moderate: Drowsiness that interferes with normal activity
	3	Severe: Drowsiness that prevents normal activity
Loss of appetite	0	Appetite as usual
	1	Mild: Eating less than usual/no effect on normal activity
	2	Moderate: Eating less than usual/interferes with normal activity
	3	Severe: Not eating at all

*Fever is defined as temperature $\geq 37.5^{\circ}\text{C} / 99.5^{\circ}\text{F}$ for oral, axillary or tympanic route, or $\geq 38.0^{\circ}\text{C} / 100.4^{\circ}\text{F}$ for rectal route. The preferred route for recording temperature in this study will be rectal/axillary.

The maximum intensity of local injection site redness/swelling will be scored at GSK Biologicals as follows:

- 0 : Absent
- 1 : ≤ 5 mm
- 2 : > 5 mm and ≤ 20 mm
- 3 : > 20 mm

The maximum intensity of fever (*oral, axillary or tympanic route*) will be scored at GSK Biologicals as follows: (*Amended 06 September 2016*)

- 0 = $< 37.5^{\circ}\text{C}$
- 1 = $\geq 37.5^{\circ}\text{C}$ to $\leq 38.0^{\circ}\text{C}$
- 2 = $> 38.0^{\circ}\text{C}$ to $\leq 39.0^{\circ}\text{C}$
- 3 = $> 39.0^{\circ}\text{C}$

All solicited local (injection site) reactions will be considered causally related to vaccination. Causality of all other AEs should be assessed by the investigator using the following question:

Is there a reasonable possibility that the AE may have been caused by the investigational vaccine?

- YES : There is a reasonable possibility that the vaccines contributed to the AE.

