	3	Severe: Drowsiness that prevents normal activity
Loss of appetite	0	Appetite as usual
	1	Mild: Eating less than usual/no effect on normal activity
	2	Moderate: Eating less than usual/interferes with normal activity
	3	Severe: Not eating at all

*Fever is defined as temperature $\geq 37.5^{\circ}\text{C}$ / 99.5°F for oral, axillary or tympanic route, or $\geq 38.0^{\circ}\text{C}$ / 100.4°F for rectal route. The preferred route for recording temperature in this study will be rectal/axillary.

The maximum intensity of local injection site redness/swelling will be scored at GSK Biologicals as follows:

0	Absent
1	≤ 5 mm
2	> 5 mm and ≤ 20 mm
3	> 20 mm

The maximum intensity of fever (oral, axillary or tympanic route) will be scored at GSK Biologicals as follows:

Grade	Temperature
0	$<37.5^{\circ}\text{C}$
1	$\geq 37.5^{\circ}\text{C}$ to $\leq 38.0^{\circ}\text{C}$
2	$>38.0^{\circ}\text{C}$ to $\leq 39.0^{\circ}\text{C}$
3	$> 39.0^{\circ}\text{C}$

The investigator will assess the maximum intensity that occurred over the duration of the event for all unsolicited AEs (including SAEs) recorded during the study. The assessment will be based on the investigator's clinical judgement.

The intensity should be assigned to one of the following categories:

- 1 (mild) = An AE which is easily tolerated by the subject, causing minimal discomfort and not interfering with everyday activities.
- 2 (moderate) = An AE which is sufficiently discomforting to interfere with normal everyday activities.
- 3 (severe) = An AE which prevents normal, everyday activities (in a young child, such an AE would, for example, prevent attendance at school/kindergarten/a day-care centre and would cause the parent(s)/LAR(s) to seek medical advice.

An AE that is assessed as Grade 3 (severe) should not be confused with a SAE. Grade 3 is a category used for rating the intensity of an event; and both AEs and SAEs can be assessed as Grade 3. An event is defined as 'serious' when it meets one of the pre-defined outcomes as described in Section 8.1.2 in the protocol.

The way the percentage of subjects will be derived will depend on the event analysed (see table below for details). As a result, the N value will differ from one table to another.

Event	N used for deriving % per subject	N used for deriving % per dose
Concomitant vaccination	All subjects with study vaccine administered	All study visits with study vaccine administered

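### Visit 1 antibody results may reach sites that are meant to be blinded to the mother's allocation while those sites are still judging safety

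*Protocol*

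**What the plan says.** - **Release of results.** Protocol 5.7.5: "The immunological assay results will be communicated to the investigator as soon as they become available". The sentence does not separate Visit 1 from Visit 4 results. It sets no hold until the last visit or unblinding. The sentences that follow it deal with non-responders.
- **What is measured at Visit 1.** Protocol Table 12 has PT, FHA and PRN tested first in all infants before dose 1, then diphtheria and tetanus.
- **Site blind.** Protocol 5.3: "The study personnel operating SBIR and the site staff will remain blinded towards the treatment allocation to subjects in study 116945". Protocol section 3 and SAP section 2 repeat this. Section 5.3 also calls the study open-label and says the group data are unblinded when study 116945 ends. It gives no date.
- **Link between mother and infant.** Protocol 5.2.2.1: "The infants enrolled in this study will be allocated to the same groups as their mothers".
- **Expected difference before dose 1.** The rationale in the Protocol synopsis says that dTpa "vaccination during pregnancy results in high pertussis antibody concentrations in infants during the period between birth and the first vaccine dose". Section 1.2.1 says the same.
- **Who judges safety.** All solicited local reactions count as related. For the rest, Protocol 8.2.3.2 says: "Causality of all other AEs should be assessed by the investigator using the following question". On the intensity of unsolicited AEs and SAEs, SAP 11.2.5 says: "The assessment will be based on the investigator's clinical judgement".

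**The concern.** The study compares infants exposed and not exposed to maternal dTpa, so the site blind protects the comparison of safety between the two groups. A pre-dose pertussis value carries information about the group by the protocol's own reasoning. The release rule, applied literally, can put that value in front of the person who decides whether a fever or an SAE was caused by vaccination and how severe an unsolicited event was.

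If the investigator forms a view of which infants were exposed, those judgements can shift in one group relative to the other. Related events and grade 3 events are tabulated by group (SAP 6.4.1), so a shift would show in the reported results. Nothing in the analysis would detect it. SAP elimination code 1060 covers a randomisation code broken at the site, not an allocation guessed from an antibody level.

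**Working it through.** The plan states no figure on this point, so there is none to reproduce. The check has three parts.

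**1. Is there a safeguard in the text?** Section 5.3 blinds the laboratory, and section 5.4.4 has the sponsor's safety review team look at blinded data. Neither restricts what the site receives. No passage in the protocol or SAP delays or masks Visit 1 results, names a separate recipient, or says that samples are tested in a batch after Visit 4. The Study Procedures Manual and laboratory manual are cited but are not part of these documents.

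**2. How long could the exposure last?** From the optimal intervals in Protocol Tables 6 to 9:

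- 2, 4, 6 months: 60 + 60 + 30 = 150 days from Visit 1 to Visit 4
- 2, 3, 4 months: 30 + 30 + 30 = 90 days
- 2-dose schedules: 60 + 30 = 90 days

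The allowed windows extend this to 78 + 78 + 48 = 204 days at most. All of these run from blood draw to last visit. A result exists only after shipment and testing, so they bound the exposure during study visits and do not estimate it.

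**3. How informative is one value?** The documents give neither a dTpa-to-Control GMC ratio (R) nor an SD (s) before dose 1. Both are assumed here: R from 3 to 10, and s from 0.4 to 0.5 on the log10 scale. The other assumptions are normal log10 concentrations, equal SDs and equal groups (340 planned in each). The standardised distance is d = log10(R)/s. The best single cut lies midway between the two means and classifies a proportion Φ(d/2) correctly.

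| R | s | d | Φ(d/2) |
|---|---|---|---|
| 3 | 0.5 | 0.477/0.5 = 0.95 | 68% |
| 3 | 0.4 | 0.477/0.4 = 1.19 | 72% |
| 5 | 0.5 | 0.699/0.5 = 1.40 | 76% |
| 5 | 0.4 | 0.699/0.4 = 1.75 | 81% |
| 10 | 0.5 | 1/0.5 = 2.00 | 84% |
| 10 | 0.4 | 1/0.4 = 2.50 | 89% |

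Guessing gives 50%. Over a wider range (R from 2 to 10, s from 0.35 to 0.55) the figure runs from 61% to 92%. It is a ceiling for one antigen, because the investigator does not know where the best cut lies. Several antigens together could add information, but without their correlation no joint figure can be given.

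**The case against.** **The study is open-label.** Table 3 says so, and the glossary says such a study uses no blind. Section 5.3 also accepts that group data will be unblinded when study 116945 ends. This narrows the point but does not remove it. The same section keeps site staff blinded to maternal allocation, and nothing ensures that study 116945 ends before Visit 1 results go out.

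**Testing may be late.** The glossary allows the end of study to fall up to 8 months after the last visit. SAP section 9 says the DTPa ELISAs used were re-developed and re-validated during the study. Both hint at late testing. If Pre-Pri results followed the last visits, the safety judgements made by then could not have been affected. That is possible but not stated.

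**The release rule may be meant for post-primary results.** Its neighbouring sentences concern non-responders, and a pre-dose sample alone cannot identify one. This is a fair alternative reading, but the wording is not limited to it.

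**Few outcomes are exposed.** Serology is read by a blinded laboratory. Parents record solicited symptoms, and the sponsor scores redness, swelling and fever from measurements. All analyses are descriptive. This stands: what remains is the causality of general symptoms and the assessment of unsolicited AEs and SAEs.

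Four stronger readings are tempting, and the documents do not support them:

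- A reader might infer that the two rules cannot both be followed. They can, if testing is late or study 116945 is already unblinded.
- A reader might infer that sites know the group for 3 to 5 months before the last visit. That interval starts at blood draw, not at receipt of a result.
- A reader might quote 75-96% under the same assumptions. That is Φ(d/√2), the chance that a random dTpa infant ranks above a random Control infant. It is not the share of infants classified correctly.
- A reader might infer damage to study 116945. Cord blood and the post-delivery dose precede Visit 1, and that study's later follow-up is not described here.

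**Conclusion.** The point holds as a risk that the current text leaves open. Following 5.7.5 as written can erode a blind that 5.3 states, at sites that judge causality and grade events. It matters only if Pre-Pri results reach a site before its safety assessments end and while the site is still meant to be blinded.

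Under the assumed ratio and SD, one pertussis antigen would suggest the right group for about 68-89% of infants. That is enough to form an impression and short of certain knowledge. How far safety judgements would move cannot be derived from the documents. The primary immunogenicity endpoints, the sample size and the confidence interval methods are untouched. The point should be corrected because the repair is simple, not because bias has been shown.

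**What to change.** Amend Protocol 5.7.5, with a cross-reference to 5.3, in three respects:

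1. Do not release individual Pre-Pri results to sites until the subject's safety data collection and investigator assessments are complete and study 116945 has been unblinded.
2. State when the site staff's blind to maternal allocation ends.
3. Keep the release of post-primary results needed to identify non-responders. Pertussis vaccine response uses the Pre-Pri value (Protocol 10.5), so while that value is held the sponsor could send the response status instead.

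Waiting for database lock as well would go further than the blind in 5.3 requires. If Visit 1 samples are already tested only after Visit 4, or the laboratory manual already holds the results, a sentence saying so, together with item 2, would be enough.

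The cost is a short text change. The one downside is that sites receive Pre-Pri values later. Identification of non-responders loses nothing, since a pre-dose sample alone cannot show non-response.

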6. STUDY VACCINES AND ADMINISTRATION

6.1. Description of study vaccine

The candidate vaccine has been developed and manufactured by GSK Biologicals.

The Quality Control Standards and Requirements for the candidate vaccine are described in separate Quality Assurance documents (e.g. release protocols, certificate of analysis) and the required approvals have been obtained.

The vaccine are labelled and packed according to applicable regulatory requirements.

Commercial vaccine are assumed to comply with the specifications given in the manufacturer's SPC.

The study vaccines, formulation and presentation is detailed in [Table 13](#).

Table 13 Study vaccines (Amended 06 September 2016)

Treatment name	Vaccines name	Formulation	Presentation	Volume to be administered*	Number of doses
Infanrix hexa	DTPa-HBV-IPV	DT>=30IU; TT>=40IU; PT=25µg; FHA=25µg; PRN=8µg; HBsAg=10µg; Inactivated Poliovirus type 1 (Mahoney strain)=40DU; Inactivated Poliovirus type 2 (MEF-1 strain)=8DU; Inactivated Poliovirus type 3 (Saukett strain)=32DU; Aluminium=700µg Al3+	The DTPa-HBV-IPV component is presented as a turbid white suspension in a pre-filled syringe.	0.5 ml *	2 or 3**
	Hib	PRP=10µg; TT~25µg Aluminium as salts = 0.12 mg	The lyophilised Hib component is presented as a white pellet in a glass vial; it must be reconstituted before use with the liquid DTPa-HBV-IPV component.		
Prevenar 13	Prevenar 13	PS1=2.2µg CRM197; PS3=2.2µg CRM197; PS4=2.2µg CRM197; PS5=2.2µg CRM197; PS6A=2.2µg CRM197; PS6B=4.4µg CRM197; PS7F=2.2µg CRM197; PS9V=2.2µg CRM197; PS14=2.2µg CRM197; PS18C=2.2µg CRM197;	Suspension for injection in a pre-filled syringe	0.5 ml	2 or 3 ***

Treatment name	Vaccines name	Formulation	Presentation	Volume to be administered*	Number of doses
		PS19A=2.2µg CRM197; PS19F=2.2µg CRM197; PS23F=2.2µg CRM197; AlPO ₄ =125µg Al3+			

*After reconstitution

** *In some countries, Infanrix hexa is given as a 2-dose schedule at 2 and 4 months of age or at 3 and 5 months of age. In other countries Infanrix hexa is given as a 3-dose schedule at 2, 4 and 6 months of age or at 2, 3 and 4 months of age as recommended by the routine immunisation programme.*

*** *Prevenar 13 is administered at the same schedule as Infanrix hexa except in some countries/regions with an Infanrix hexa 3-dose schedule where Prevenar 13 is given as a 2-dose schedule at 2 and 4 months of age as a part of the routine immunisation programme.*

(Amended 06 September 2016)

